### **Study Title**

# The Effects of Custom-Designed 3D Printed and CAD-CAM Insole on Foot Posture, Plantar Pressure Distribution, and Satisfaction in Individuals with Flexible Pes Planus

### **Study Purpose and Importance**

The purpose of this study is to investigate the effects of custom-designed insoles manufactured using Computer Numerical Control (CNC) and 3D printing technologies on plantar pressure distribution, foot posture, plantar force distribution, foot pain, and satisfaction in individuals diagnosed with flexible pes planus. This research aims to contribute to evidence-based practice in orthotic interventions.

### **Study Site**

The study will be conducted at the Orthotics and Prosthetics Application and R&D Laboratories of the Faculty of Health Sciences at Ondokuz Mayıs University.

### **Study Period**

The study will be carried out between April 1, 2025 and December 31, 2025.

## **Study Design**

This study will be conducted as a randomized controlled trial.

## **Study Population and Sample**

The study population consists of individuals aged between 18 and 55 who have been clinically diagnosed with flexible pes planus and referred with a physician's prescription for custom insoles to the Orthotics and Prosthetics Department at Ondokuz Mayıs University.

Sample size was calculated using the G\*Power 3.1.9.4 software. Based on the study by Ünver and Bek (2014) that investigated the effects of insole use on plantar contact area and pressure distribution, with an alpha of 0.05, an effect size of 1.53, and a power of 0.95, the required sample size was determined to be 13 individuals per group, for a total of 26 participants. To increase statistical power and account for potential dropouts, the study will include 40 participants, divided equally into two groups (20 in each).

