## **Inclusion** Criteria

Age between 18 and 55

Diagnosed with unilateral or bilateral flexible pes planus

At least +6 on the Foot Posture Index (FPI)

 $\geq$ 5° subtalar pronation angle during standing

No foot or lower limb treatment in the last 6 months

Voluntary participation with written and verbal informed consent

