## **Randomization and Groups**

Participants will be randomly assigned to one of two groups using a simple randomization method (drawing lots).

Group 1 will receive insoles produced using CNC technology.

Group 2 will receive insoles produced via 3D printing.

Each participant will be evaluated before and after 8 weeks of insole use.

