## **Data Collection Tools and Assessment Methods**

Participants will be evaluated at baseline and after 8 weeks of insole use. The following tools will be used:

Foot Posture Index (FPI): Assesses the degree of pes planus; individuals scoring +6 or higher are eligible.

Subtalar Angle Measurement: Conducted with a goniometer while standing barefoot.

VAS-FA (Visual Analog Scale – Foot and Ankle): Evaluates pain and functional limitations specifically related to the foot and ankle. The scale ranges from worst to best function and pain levels, based on participant self-reporting.

Plantar Pressure Analysis: Using a sensor-based platform for both static and dynamic measurements of plantar contact and pressure distribution.

Quebec User Evaluation of Satisfaction with Assistive Technology (QUEST 2.0): Measures user satisfaction with the orthotic device.

Orthotics and Prosthetics Users' Survey (OPUS) – Lower Extremity Functional Scale: Evaluates lower limb functionality and daily mobility performance.

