# **Data Collection Procedure**

Each participant's group will be determined by random draw.

- 20 participants will receive CNC-produced insoles.
- 20 participants will receive 3D-printed insoles.

Data will be collected through:

- Face-to-face administration of surveys
- Pressure mapping via pedobarographic analysis
- Standardized clinical measurement protocols

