## **Statistical Analysis**

Statistical analysis will be conducted using **IBM SPSS 22**. Descriptive statistics (mean  $\pm$  SD) will be used for demographic and clinical variables.

- Normality testing: Shapiro-Wilk test
- Within-group comparisons (pre- and post-intervention): Paired t-test
- Between-group comparisons: Independent samples t-test
- Repeated measures (time × group interaction): Repeated Measures ANOVA
- Categorical variables: Chi-square and Fisher's Exact Test

A significance level of p < 0.05 will be considered statistically significant.

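### Does borrowing an effect size of 1.53 from a study of insole use undermine the 0.95 power stated for the CNC versus 3D-printed comparison?

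*Combined protocol and SAP*

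**What the plan says.** Under Study Population and Sample, the combined protocol and SAP relies on one earlier study that "investigated the effects of insole use on plantar contact area and pressure distribution, with an alpha of 0.05, an effect size of 1.53". With "a power of 0.95, the required sample size was determined to be 13 individuals per group, for a total of 26 participants", the calculation is complete. The section then adds a margin: "To increase statistical power and account for potential dropouts, the study will include 40 participants", 20 in each group. It does not name the test, the sidedness, the plantar variable, or the means and SDs behind 1.53.

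Under Randomization and Groups and Data Collection Procedure, both arms are active: "20 participants will receive CNC-produced insoles", and the other group "will receive insoles produced via 3D printing". There is no arm without an insole.

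The assessment section includes a pressure platform for "static and dynamic measurements of plantar contact and pressure distribution", the same outcome family as the cited study. Statistical Analysis lists "Between-group comparisons: Independent samples t-test", a time by group repeated measures ANOVA, and mean with SD for clinical variables. It sets significance at p < 0.05.

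**The concern.** An effect of wearing an insole and a difference between two insoles are different quantities. The first may compare insole with no insole, or before with after. The second compares two active devices that share a purpose and differ in how they are made, and one would usually expect it to be smaller. If 1.53 is an effect of the first kind, the 0.95 power belongs to a comparison that this trial does not randomise.

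The stated power is also the plan's only statement of what the between-group comparison can detect. If its input has no bearing on CNC versus 3D printing, a reader might expect high sensitivity where there is little, and take a non-significant result as more informative than it is. The plan does not mention a confidence interval for the between-group difference, which seems to add to the difficulty.

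**Working it through.** **Inputs from the sample size section:** alpha 0.05, standardised effect d = 1.53, target power 0.95, 1:1 allocation, 13 per group required, 20 per group enrolled. Two-sided testing is assumed because the plan does not say.

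**Step 1: reproduce the plan's figure.** For two independent groups of n, power is the probability that a noncentral t variable with 2n − 2 degrees of freedom and noncentrality d√(n/2) falls beyond ±t(0.975, 2n − 2).

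- n = 12: power 0.947, short of 0.95.
- n = 13: noncentrality 1.53 × √6.5 = 3.90; power 0.962.

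The smallest adequate n is 13, as stated. Other readings do not fit: a one-sided independent t-test needs 11 per group, and a two-sided paired t-test needs 8 in total. So 1.53 was used as a between-group difference, which agrees with the independent t-test in Statistical Analysis.

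**Step 2: what the enrolled sample gives at 1.53.** With n = 20 the noncentrality is 1.53 × √10 = 4.84 and power is 0.997. Enrolment is 40/26 = 1.54 times the calculated total.

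**Step 3: how far the difference can fall.** Solving the same power function for d, with one value per person and one outcome:

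| Analysed per group | d at 95% power | Below 1.53 by | d at 80% power | Below 1.53 by |
|---|---|---|---|---|
| 20 | 1.170 | 1 − 1.170/1.53 = 23.5% | 0.909 | 1 − 0.909/1.53 = 40.6% |
| 16 (20% dropout, an assumption) | 1.318 | 13.9% | 1.024 | 33.1% |

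**Step 4: smaller differences.** The documents give no CNC versus 3D-printed difference, so these values of d are assumptions:

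| d | Power, 13 per group | Power, 20 per group | n per group for 0.95 |
|---|---|---|---|
| 0.3 | 0.114 | 0.152 | 290 |
| 0.5 | 0.232 | 0.338 | 105 |
| 0.8 | 0.499 | 0.693 | 42 |
| 1.0 | 0.687 | 0.869 | 27 |
| 1.2 | 0.835 | 0.959 | 20 |
| 1.53 | 0.962 | 0.997 | 13 |

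**Step 5: can a null result be read?** The 95% interval for the between-group difference is the difference ± t(0.975, 2n − 2) × pooled SD × √(2/n). If the planned means and SDs are given by group with n, a reader has all its terms. The half-width is 0.640 SD with 20 per group and 0.722 SD with 16.

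**Step 6: the other planned test.** For the time by group test with equal variances at both visits, the SD of change is √(2(1 − ρ)) times the single-visit SD, where ρ is the pre-post correlation. The 80% detectable difference with 20 per group is then 0.909 × √(2(1 − ρ)): 1.08 at ρ = 0.3, 0.91 at 0.5, 0.70 at 0.7 and 0.57 at 0.8. These correlations are assumptions. No single figure can therefore replace 1.53 without choices that the documents do not make.

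**The case for a change.** The strongest case for a change is that borrowing an effect size needs a stated link to the comparison being tested, and here there is none. The source is described only as a study of insole use, both arms wear insoles, and the calculation demonstrably treats 1.53 as the difference between them. Raising enrolment to 40 widens the margin but supplies no reason to expect a difference of this size. Even 1.17 SD is large for two active devices, and at an assumed 0.5 SD power is about one third. The remedy would be cheap: state the detectable difference, promise an interval, and warn against reading non-significance as sameness.

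The description of the gap stands. A sentence giving the contrast, variable, means and SDs behind 1.53 would be a courtesy to readers, and reporting the between-group difference with its interval is good practice.

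The rest does not carry. Whether the cited study compared insole types, insole with none, or before with after cannot be learned from the documents, so a mismatch is possible but not shown. The outcome family is given and matches the planned pressure analysis; only the exact variable is missing. The interval follows from the planned summaries, as Step 5 shows. The plan makes no claim of equivalence, so a warning against one guards against something it does not propose. A replacement power sentence would need a named outcome, one value per person (bilateral cases are eligible: "Diagnosed with unilateral or bilateral flexible pes planus") and a choice between the t-test and the time by group test. Those are separate questions.

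**Conclusion.** No change to the plan is needed. The power statement is conditional on a difference of 1.53 SD, says so openly, and is correct on that condition: 0.962 at 13 per group and 0.997 at 20. What is missing is the reason for choosing 1.53. Supplying it would alter no sample size, test, procedure or result, and a reader can work out from 20 per group what the trial can detect: 0.91 SD with 80% power and 1.17 SD with 95%, or 1.02 and 1.32 SD if 16 per group are analysed.

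This assumes two-sided independent t-tests at 0.05, one value per person and a single outcome; the 20% dropout is also an assumption. The conclusion would have to be revisited if the cited study were shown to report 1.53 for a different contrast, which the documents do not allow one to judge. Whatever its source, the trial should be read as one that can reliably find large differences between the two manufacturing methods and not moderate ones.

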## **Inclusion** Criteria

Age between 18 and 55

Diagnosed with unilateral or bilateral flexible pes planus

At least +6 on the Foot Posture Index (FPI)

 $\geq$ 5° subtalar pronation angle during standing

No foot or lower limb treatment in the last 6 months

Voluntary participation with written and verbal informed consent

## **Exclusion** Criteria

History of lower extremity surgery

Active athlete status

Pregnancy or malignancy

Neurological or orthopedic conditions limiting physical activity

More than 1 cm lower limb length discrepancy

Receiving any other treatment for pes planus

## **Randomization and Groups**

Participants will be randomly assigned to one of two groups using a simple randomization method (drawing lots).

Group 1 will receive insoles produced using CNC technology.

Group 2 will receive insoles produced via 3D printing.

Each participant will be evaluated before and after 8 weeks of insole use.

## **Data Collection Tools and Assessment Methods**

Participants will be evaluated at baseline and after 8 weeks of insole use. The following tools will be used:

Foot Posture Index (FPI): Assesses the degree of pes planus; individuals scoring +6 or higher are eligible.

Subtalar Angle Measurement: Conducted with a goniometer while standing barefoot.

VAS-FA (Visual Analog Scale – Foot and Ankle): Evaluates pain and functional limitations specifically related to the foot and ankle. The scale ranges from worst to best function and pain levels, based on participant self-reporting.

Plantar Pressure Analysis: Using a sensor-based platform for both static and dynamic measurements of plantar contact and pressure distribution.

Quebec User Evaluation of Satisfaction with Assistive Technology (QUEST 2.0): Measures user satisfaction with the orthotic device.

Orthotics and Prosthetics Users' Survey (OPUS) – Lower Extremity Functional Scale: Evaluates lower limb functionality and daily mobility performance.

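### Does listing QUEST 2.0 under the shared baseline and week-8 schedule commit the trial to a satisfaction analysis that cannot be interpreted?

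*Combined protocol and SAP*

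**What the plan says.** Data Collection Tools and Assessment Methods gives the timing once, for the study as a whole: "Participants will be evaluated at baseline and after 8 weeks of insole use. The following tools will be used". Six tools follow: FPI, subtalar angle, VAS-FA, plantar pressure, QUEST 2.0 and OPUS. The QUEST entry reads "Measures user satisfaction with the orthotic device" and names no visit.

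Randomization and Groups places the first assessment ahead of insole use: "Each participant will be evaluated before and after 8 weeks of insole use". The eligibility criteria make a comparable device in current use unlikely. Participants must have had "No foot or lower limb treatment in the last 6 months", and they are excluded if "Receiving any other treatment for pes planus" applies.

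Data Collection Procedure mentions "Face-to-face administration of surveys" without saying at which visit. Statistical Analysis lists a paired t-test for change within groups, an independent-samples t-test between groups and a repeated-measures ANOVA for time × group. It ties none of these to a particular outcome. QUEST is not named anywhere outside the list of tools.

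**The concern.** A satisfaction questionnaire about a device can be answered sensibly only by someone who has used the device. If all six tools are applied at both visits, each of the 40 participants would be asked at baseline to rate an insole not yet used. The answer would be blank, or would describe something else, such as an expectation or an older device.

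If that score then entered the paired t-test, the result would be labelled a change in satisfaction although the starting value did not measure satisfaction with the study insole. Satisfaction is in the title and is one of the outcomes in the stated purpose, which concerns effects "on plantar pressure distribution, foot posture, plantar force distribution, foot pain, and satisfaction in individuals diagnosed with flexible pes planus". No outcome is designated primary, so a spurious pre-post satisfaction result could receive as much attention as any other finding.

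**Working it through.** The plan gives no figure for QUEST. Its one calculated figure, 13 per group in Study Population and Sample, reproduces with a two-sided two-sample t-test at d = 1.53 and alpha 0.05 (power 0.962 at n = 13). It does not depend on when QUEST is collected. What remains is to ask what each listed test would estimate.

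**Inputs.** Two groups of 20 (Study Population and Sample), two visits (Randomization and Groups) and three listed tests for mean scores (Statistical Analysis). Let Y be the week-8 QUEST score and B any baseline QUEST score. Subscripts 1 and 2 denote the CNC and 3D-printed groups.

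**Step 1: what each test estimates.**

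| Listed test | Quantity estimated | Needs B? | Reading for QUEST |
|---|---|---|---|
| Independent samples, week 8 | E[Y₁] − E[Y₂] | No | Valid comparison of satisfaction |
| Time × group ANOVA | E[(Y₁ − B₁) − (Y₂ − B₂)] | Yes | See step 2 |
| Paired, within group | E[Y] − E[B] | Yes | Not a change in satisfaction with the insole |

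**Step 2: the interaction test.** With two groups and two visits, the interaction F equals the square of the two-sample t on Y − B. Its target is

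E[(Y₁ − B₁) − (Y₂ − B₂)] = E[Y₁ − Y₂] − (E[B₁] − E[B₂]).

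If baseline is rated before the allocation is known, randomisation gives E[B₁] = E[B₂]. The last term is then zero and the target is the week-8 difference. The documents do not state that order, so this is an assumption. Under it, the interaction test carries along an irrelevant baseline but is not biased by it.

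**Step 3: the ways the plan could be carried out.**

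- *QUEST is given at week 8 only.* No B exists. The paired and interaction tests cannot be computed, and the independent-samples test is the only one left.
- *QUEST is offered at baseline and left blank.* The outcome is the same.
- *QUEST is completed at baseline.* All three tests can be computed. The week-8 comparison is still available and still valid. Only the paired test has no useful meaning, and it misleads only if an analyst also chooses to run and report it for satisfaction.

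**Step 4: which of these the text requires.** The schedule sentence fixes the visits, and the next sentence introduces the instruments. That every instrument is used at every visit is an inference. The QUEST entry limits itself, because it presupposes a user and a device, and before insole use there is neither. Statistical Analysis is a general list and does not send QUEST to the paired test. The problem therefore needs two further decisions that the plan does not make: collecting ratings of a device not yet used, and testing the change in them.

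**The case for a change.** The best argument for a change is that a protocol should not leave staff or analysts to guess. QUEST sits in a list headed by a two-visit schedule, no exemption is written, and no other section supplies its visit or its test. Satisfaction is a headline outcome and a clarification would cost only two lines. Each of these points is true, and if a within-group test on QUEST were run it could not be read as change in satisfaction with the insole.

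What does not follow is that the plan contains a faulty analysis. The test at fault is never assigned to QUEST, while the appropriate one is already listed. A count of 40 wasted baseline forms holds only on the most literal reading; if week 8 alone is meant, the count is zero. The week-8 between-group result would be the same with or without the clarification. That no outcome is linked to a test is a wider feature of Statistical Analysis, and it should be judged there, not through this single instrument.

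**Conclusion.** No change is needed. The plan omits QUEST's visit and test, and the content of the instrument supplies both: satisfaction with an insole is asked after the insole has been worn, and the groups are compared at that point. The omission concerns one of six tools and one of the five outcomes in the stated purpose. It alters no stated number and does not harm the week-8 comparison of CNC with 3D-printed insoles.

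This rests on two assumptions. Staff and analysts are taken to read QUEST as its description implies. If the interaction test were nonetheless applied to it, baseline is taken to have been rated before allocation was known. If the first fails, the damage is confined to a within-group satisfaction result that a reader should disregard; the week-8 comparison stands in either case.

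### Foot pain is a stated effect, but the plan separates no pain score from the one scale that covers both pain and function

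*Combined protocol and SAP*

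**What the plan says.** Study Purpose and Importance lists five effects of the two insole types: "plantar pressure distribution, foot posture, plantar force distribution, foot pain, and satisfaction". Foot pain is one of them, and plantar force is listed separately from plantar pressure.

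Under Data Collection Tools and Assessment Methods, pain appears only in the VAS-FA entry. That entry gives two descriptions: "Evaluates pain and functional limitations specifically related to the foot and ankle" and "The scale ranges from worst to best function and pain levels, based on participant self-reporting". It mentions no pain item, subscore or scoring rule. Function also has an instrument of its own, the OPUS lower extremity scale: "Evaluates lower limb functionality and daily mobility performance".

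The platform entry in the same section reads "Using a sensor-based platform for both static and dynamic measurements of plantar contact and pressure distribution", and Data Collection Procedure has "Pressure mapping via pedobarographic analysis". Force is not named again after the purpose.

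Statistical Analysis lists paired and independent t-tests, a repeated measures ANOVA for time by group, and tests for categorical data. It ties none of them to an instrument or a score.

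**The concern.** A reader cannot tell which number will answer the foot-pain question. The only description offered puts pain and function on the same scale. If one combined score is tested and the result is reported as pain, two errors are possible:

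- A true pain difference between CNC and 3D-printed insoles can be averaged down by function items that moved less.
- A difference in function with no difference in pain can move the score and be reported as pain relief.

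OPUS does not resolve this. It allows function to be examined separately, but it does not isolate pain. Because the rule is open, the choice between a total and selected items could also be made after the data are seen.

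Plantar force raises a smaller point of the same kind: it is named as an effect, but no variable is named for it.

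**Working it through.** **The plan's own figure.** Study Population and Sample gives 13 per group for an effect size of 1.53, alpha 0.05 and power 0.95. A two-sided two-sample t-test (noncentral t) has power 0.947 at 12 per group and 0.962 at 13, so 13 reproduces. That effect size comes from a study of plantar contact area and pressure. It says nothing about pain, and this point leaves the sample size arithmetic unchanged.

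**Inputs from the documents.** 20 per group; independent samples t-test; significance at p < 0.05, taken here as two-sided.

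**Assumed inputs, because the documents give none.** Pain weight w in a combined score; equal SDs for the pain and function parts; correlation r between them; pain difference d = 0.909 SD, chosen because it gives 80% power on a pain score at 20 per arm; function difference equal to k times the pain difference.

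**Formula.** Standardised difference on the combined score:

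D = d × [w + (1 − w)k] / sqrt(w² + (1 − w)² + 2w(1 − w)r)

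With w = 0.5 and r = 0.5 the denominator is sqrt(0.25 + 0.25 + 0.25) = 0.866.

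| Function shift relative to pain (k) | D | Power, 20 per arm |
|---|---|---|
| 0 | 0.909 × 0.50 / 0.866 = 0.525 | 37% |
| 0.5 | 0.909 × 0.75 / 0.866 = 0.787 | 68% |
| 0.75 | 0.909 × 0.875 / 0.866 = 0.918 | 81% |
| 1 | 0.909 × 1.00 / 0.866 = 1.050 | 90% |

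The comparison value is 80% on the pain score alone. The combined score therefore loses power when function moves clearly less than pain, breaks even near k = 0.73 (from 0.5 + 0.5k = 0.866), and gains when the two move alike.

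**Sensitivity to r and w.**
- k = 0, w = 0.5: 41% at r = 0.3 and 33% at r = 0.7.
- k = 0, w = 0.33, r = 0.5: 18%.
- k = 1, w = 0.5: 94% at r = 0.3 and 86% at r = 0.7.

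**The reverse case.** Pain does not differ and function differs by 1.0 SD. With w = 0.5 and r = 0.5, D = 0.5 × 1.0 / 0.866 = 0.577. The combined score is significant 43% of the time although pain is the same in both arms.

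**Plantar force.** No arithmetic applies. The purpose lists pressure and force as separate items, while the platform entry covers only "measurements of plantar contact and pressure distribution".

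**The case against.** The strongest reply is that no passage says a VAS-FA total will be analysed. The entry names two constructs, and Statistical Analysis links no test to any score. A reader might infer that a pain difference *is* diluted under this plan. The documents do not support that, because dilution needs both a combined score and a function shift clearly smaller than the pain shift. If the two shift equally, the combined score has more power than pain alone (90% against 80%). This part of the reply stands, and the point is conditional for that reason. It does not remove the gap, since the plan still leaves the pain score undefined. Nor does it touch the reverse error: extra power on a combined score is not evidence about pain.

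A second reply is that the documents do not describe the VAS-FA's items, so a separable pain score cannot be taken for granted. That also stands, and the fix allows for it.

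A third is that foot pain is absent from the study title, is not marked as primary and does not drive the sample size. This limits the weight of the point. Foot pain nevertheless remains one of five stated effects.

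A fourth is that the planned time by group ANOVA already uses baseline values. That is true, but the ANOVA inherits whichever score is entered, so it does not separate pain from function.

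On force, a reader might infer that this part of the purpose cannot be answered at all. The documents do not show that. The platform records contact and pressure, from which a force variable might be derived; the plan simply does not name one.

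**Conclusion.** The concern holds as a gap in outcome definition. Foot pain is a stated effect, its only instrument is described as covering pain together with function, and no pain score is separated from it. A test on a combined score could not by itself support a conclusion about pain.

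The size depends on inputs that the documents do not give. With equal weights, equal SDs, correlation 0.5 and a pain difference of 0.91 SD, power on the combined score runs from 37% to 90% as the function shift goes from none to equal, against 80% on pain alone. The chance that a 1.0 SD function-only difference reaches significance is 43%. These figures show that the choice of score can decide the conclusion at 20 per arm; they do not predict what this trial will find.

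The force item is a matter of naming a variable and carries no figure.

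**What to change.** - In Data Collection Tools and Assessment Methods and in Statistical Analysis, define the foot-pain outcome as the VAS-FA pain-item score at 8 weeks, compared between groups with adjustment for the same score at baseline.
- Report any VAS-FA total only as a combined measure of pain and function, and base no statement about pain on it.
- If the version in use has no separable pain items, restate the purpose as foot pain and function combined.
- Minor clarification: name the platform variable that represents plantar force, or remove force from the purpose.

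Cost: if the pain items can be separated, these are edits to the text, with no extra visits or participants and no change to the sample size calculation. The small downside is that a score from fewer items may be noisier than a total.
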